4.3 Study Enrollment Procedures

- 4.3.1 Prior to implementation of this protocol, and any subsequent full version amendments, each site must have the protocol and the protocol consent form approved, as appropriate, by their local institutional review board (IRB)/ethics committee (EC) and any other applicable regulatory entity (RE). Upon receiving final approval, sites will submit proof of IRB approval and site-specific informed consent forms (ICFs) to [name] ([contact]) and UCLA-Westwood (UCLA-WW) regulatory staff ([name], [contact]). They will ensure that all of the required documents have been received.

All site-specific and primary UCLA-WW IRB documents should be retained in the site's regulatory files.

Upon receiving final IRB/EC and any other applicable RE approvals for an amendment, sites should implement the amendment immediately. Sites should submit proof of approved amendments for their site via email to [name] and UCLA-WW regulatory staff ([name]). A copy of the amendment should be retained in the site's regulatory files.

Once a candidate for study entry has been identified, details will be carefully discussed with the subject. The subject (or, when necessary, legal guardian if the subject is under guardianship) will be asked to read and sign the approved protocol consent form.

For subjects from whom a signed informed consent has been obtained, a CTSI-PLACE Study Screening Checklist must be entered through REDCap, the study database.

4.3.2 Subject Registration

For subjects from whom informed consent has been obtained, but who are deemed ineligible or who do not enroll into the initial protocol step, a CTSI-PLACE Study Screening Failure Result form must be completed and keyed into the database.

- 4.4 Coenrollment Guidelines. Coenrollment into any study requires study team approval.

- 5.0 Study Medications. No medications are being given as part of this study, but medications are relevant to the study questions and should be documented at each study visit.

5.0.1 Concomitant Medications

Whenever a concomitant medication is initiated or a dose changed, investigators must document the change in source documents and CRFs.

5.0.2 Required Medications

All antiretroviral regimens are acceptable.

5.0.3 Prohibited Medications

There are no prohibited medications specific to this study.

6.0 CLINICAL, LABORATORY, AND ENDOTHELIAL FUNCTION EVALUATIONS

6.1 Schedule of Events

Evaluation	Screening	Entry Week 0	Chart abstraction	Study Visit	Premature Study Discontinuation ¹
Week			Week 24	Week 52 ²	
Window			±28 days	±28 days	
Documentation of HCV Status*	X			X	X
Documentation of HIV-1 Infection*	X				
Medical History/Medication History	X	X	X	X	X
Clinical Assessment ³	X	X		X	X
Concomitant Medications		X	X	X	X
Hematology/Chemistry/Liver Function Tests*		X		X	X
INR*		X		X	X
CD4+/CD8+ T-Cell Counts*	X		X	X	X
Plasma HIV-1 RNA*	X		X	X	X
Serum HCV RNA (screening)*	X				
Serum HCV RNA (on-study)*			X	X	X
HCV Genotype Test*		X			
Hemoglobin A1c*	X			X	X
Pregnancy test	X			X	X
Liver biopsy results*		X		X	X
Fasting Stored Serum/Plasma for Batched CVD Biomarkers ⁴		X		X	X
Stored Serum/Plasma for Future Studies		X		X	X
Peripheral Arterial Tonometry		X		X	X

*Longitudinal values of these laboratory tests, if available, will be obtained via chart abstraction from the participants' medical records. Specific tests will be performed in real-time only as indicated in the instructions for evaluations. INR should be collected for HCV coinfecting subjects only. Hemoglobin A1c should be collected for diabetic subjects only. Availability of liver biopsy results will be assessed and, if available, results recorded from the medical record. Liver biopsy will not be performed for this study. For HIV monoinfected subjects, screening HCV antibody should be performed at the week 52 visit.

¹All subjects enrolled in the study for a minimum of 3 months but less than 1 year should have a premature study discontinuation visit, including repeat PAT and biomarker testing. If this testing occurs while on HCV treatment, concurrent treatment status should be documented in source documents and on the CRF. For subjects enrolled in the study for fewer than 3 months, telephone interview and chart abstraction should be conducted for clinical data from the time of study entry to study discontinuation.

²For coinfecting subjects who initiate HCV treatment, week 52 assessments should occur at 4 weeks after end of treatment (EOT), but no earlier than 3 weeks and no later than 8 weeks after EOT. If not available in the medical record, a serum HCV RNA should be performed at 4 weeks after EOT. The medical record should be reviewed and HCV RNA at 12 and 24 weeks after EOT should be recorded.

³Required elements for clinical assessments are described in section 6.3.

⁴Batched biomarkers will include fasting lipid panel, fasting insulin, fasting glucose, hsCRP, IL-6, D-dimer, sICAM-1, sE-selectin, and Lp-PLA2. Fasting insulin and fasting glucose should only be performed on non-diabetic subjects. Plasma will also be tested for microparticles.

6.2 Timing of Evaluations

6.2.1 Screening Evaluations

Screening evaluations must occur within 4 weeks prior to the subject starting any study procedures.

6.2.2 Entry Evaluations

Entry evaluations must occur within 4 weeks of the screening visit.

6.2.3 Post-Entry Evaluations

On-Study Evaluations

Evaluations should occur after registration. The week 24 visit consists only of review of the medical record and abstraction of data from the time since study entry. The week 52 study visit should be scheduled within the visit window. For HCV-infected subjects who initiate HCV treatment, the week 52 visit should occur at 4 weeks after end of HCV treatment, but not earlier than 3 weeks and no later than 8 weeks after EOT.

Study Completion Evaluations

Clinical assessment and laboratory evaluation, as outlined in section 6.1, will be performed at study completion (week 52 visit).

6.2.4 Discontinuation Evaluations

Evaluations for Registered Subjects Who Do Not Start Study Procedures

All CRFs must be completed and keyed for the period up to and including week 0.

Subjects who discontinue the study prior to 1 year

Subjects who permanently discontinue study prior to 1 year and have been enrolled for at least 3 months will have a study discontinuation visit including

repeat biomarker and PAT testing. Subjects on study for < 3 months should be contacted by phone for a telephone interview and have medical record review and data abstraction for clinical events, including new diagnoses and change in medications, since the time of study entry.

Pregnancy

Female subjects who conceive after study entry will be discontinued from the study.

6.3 Instructions for Evaluations

All clinical, laboratory, and tonometry information required by this protocol is to be present in the source documents. All stated evaluations are to be recorded on the CRF and keyed into the database unless otherwise specified. This includes events that meet the following International Conference on Harmonisation (ICH) definitions for a serious adverse event (AE):

- Results in death
- Life-threatening
- Requires inpatient hospitalization or prolongation of existing hospitalization
- Results in persistent or significant disability/incapacity
- Congenital anomaly/birth defect
- Other important medical event (may not be immediately life-threatening or result in death or hospitalization, but may jeopardize the patient or may require intervention to prevent one of the events listed above).

6.3.1 Documentation of HIV-1 Infection

Please refer to section 4.0 regarding assay requirements for HIV-1 documentation. Year of HIV diagnosis and nadir CD4 cell count should be recorded on the CRF.

6.3.2 Documentation of HCV Infection

Please refer to section 4.0 regarding requirements for HCV documentation for both HIV/HCV coinfecting and HIV mono-infected subjects. Year of HCV diagnosis and mode of HCV transmission should be recorded on the CRF.

6.3.3 Documentation of Liver Biopsy

If a liver biopsy has been performed within 5 years prior to study entry or is performed during the course of the study, documentation of date of biopsy, liver fibrosis and activity scores, steatosis measurement, and scoring system (e.g. METAVIR, Knodell, etc.) should be recorded on the CRF.

6.3.4 Medical History

The medical history must include all diagnoses, year of initial diagnosis, and status of diagnosis (ongoing condition or not). Any allergies to medications and their formulations must be documented. Record tobacco, alcohol, and drug use history on the CRF. Record menopause status on the CRF.

6.3.5 Medication History

A medication history must be present, including start and stop dates. All current medications should be recorded. The table below lists the medications that must be included in the history.

Medication Category	Complete History or Timeframe	Record on CRFs
HIV treatment	Within 120 days prior to entry	Yes
HCV treatment	Complete History	Yes
Other prescription drugs	Within 42 days prior to entry	Yes
Non-prescription drugs	Within 42 days prior to entry and taken daily for at least 7 days	Yes
Complementary and alternative medicines	Within 42 days prior to entry and taken daily for at least 7 days	Yes

6.3.6 Clinical Assessments

Vital Signs

Blood pressure and heart rate will be recorded at screening and entry.

Height

Height will be measured at entry.

Weight

Weight will be measured at entry and week 52 visit.

Waist Circumference

Waist circumference will be measured at entry and week 52/study discontinuation visit. Measure waist circumference at level of iliac crest in centimeters (cm).

Signs and Symptoms

At entry, all signs and symptoms that occurred within 42 days before entry must be recorded. At week 52/study discontinuation visit, all signs and symptoms that occurred within 42 days prior must be recorded.

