PROCEDURES	Group A (HIV/HCV coinfecting) Baseline: All subjects will undergo baseline endothelial function testing and laboratory assays on study entry. Follow-up: Subjects who do not initiate HCV treatment will have follow-up endothelial function and laboratory testing at 1 year. Subjects who initiate HCV treatment will have follow-up endothelial function and laboratory testing at 4 weeks after completing HCV treatment. Group B (HIV monoinfected) Baseline: All subjects will undergo baseline endothelial function testing and laboratory assays on study entry. Follow-up: All subjects will have follow-up endothelial function and laboratory testing at 1 year.

¹ Group A, HIV/HCV coinfectd; Group B, HIV monoinfected

² Baseline assessments as described in section 6.1, including vital signs, medical history, medications, medical record abstraction, serum/plasma collection and processing for laboratories and storage, and PAT testing

³ HCV treatment may be initiated at any point following study entry

⁴ The chart abstraction visit will consist of data abstraction by study staff from the medical record for the preceding 6 months (from time of study entry).

⁵ Follow-up assessments as described in section 6.1. PAT and biomarker testing at 1 year for all subjects except those that initiate HCV treatment. For those that initiate HCV treatment, PAT and biomarker testing should occur at 4 weeks after end of HCV treatment. HCV-treated subjects should then continue to be followed until 24 weeks after end of HCV treatment and HCV viral load at 12 and 24 weeks after end of HCV treatment recorded (through medical record abstraction).

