9.2.2 Secondary Endpoints

9.2.2.1 Insulin resistance by HOMA-IR (fasting insulin ($\mu\text{U/mL}$) x fasting glucose (mg/dl)/405) at baseline and week 52.

9.2.2.2 Framingham risk score for 10-year CHD and 10-year CVD risk at baseline and week 52.

9.2.2.3 Cardiovascular biomarkers (fasting lipid panel, hsCRP, IL-6, D-dimer, sICAM-1, sE-selectin, Lp-PLA2) at baseline and week 52.

9.2.2.4 RHI by PAT at week 52

9.2.2.5 Change in RHI , biomarkers, HOMA-IR, and FRS from baseline to week 52.

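### Week-52 Framingham risk score and its change are secondary endpoints, but section 6.3.6 specifies blood pressure only at screening and entry

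*Combined protocol and SAP*

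**What the plan says.** Section 9.2.2.2 lists as a secondary endpoint "Framingham risk score for 10-year CHD and 10-year CVD risk at baseline and week 52". Section 9.2.2.5 adds "Change in RHI , biomarkers, HOMA-IR, and FRS from baseline to week 52". Neither gives an equation, a version, a list of inputs or a reference for the score.

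On blood pressure, section 6.3.6 says "Blood pressure and heart rate will be recorded at screening and entry". The same section names the follow-up visit for other measurements. For weight it says "Weight will be measured at entry and week 52 visit", and for waist circumference and for signs and symptoms it names week 52 or study discontinuation.

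The Schedule of Events in 6.1 ticks the Clinical Assessment row at screening, entry, week 52 and premature discontinuation. Footnote 3 to that table leaves the required elements to section 6.3.

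**The concern.** A score defined at two time points needs its inputs at both. If the FRS version used takes measured systolic pressure, a site that follows 6.3.6 as written will have no follow-up value for it. The week-52 score is then missing, or is computed with the entry pressure carried forward. Carrying it forward fixes the pressure contribution to change in FRS at zero, whatever happened to the participant's pressure during the year.

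A third possibility is that some sites take a reading because of the schedule tick and others do not. The endpoint would then mix measured and missing pressures by site. A pressure not recorded at the visit cannot be recovered later.

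**Working it through.** No figure in the plan needs reproducing. The check is whether any passage supplies a week-52 blood pressure.

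- **Section 6.3.6, vital signs.** Screening and entry only.
- **Section 6.1, Clinical Assessment row.** Ticked at week 52 and discontinuation, but footnote 3 sends the reader to 6.3, and so back to 6.3.6.
- **Section 6.2.3, study completion.** Says that clinical assessment takes place at week 52 as set out in 6.1. This leads through the same footnote to 6.3.6.
- **Schema footnotes.** For baseline, footnote 2 reads "Baseline assessments as described in section 6.1, including vital signs". For follow-up, footnote 5 reads "Follow-up assessments as described in section 6.1" and does not name vital signs.
- **Chart abstraction of laboratory values.** The asterisk note in 6.1 reads "Longitudinal values of these laboratory tests, if available, will be obtained via chart abstraction". It applies to starred rows, and Clinical Assessment is not starred.
- **Week-24 record review.** Schema footnote 4 and section 6.2.3 describe abstraction that is not limited to laboratory tests. They concern week 24 and do not name blood pressure.
- **Section 6.3.13, PAT.** A cuff is inflated above systolic pressure, but nothing asks for a pressure value to be recorded.
- **Section 6.3, opening paragraph.** Stated evaluations go on the CRF. A week-52 pressure is not a stated evaluation.

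No passage orders a week-52 pressure, and none forbids one. Other plausible inputs do have a week-52 source: the fasting lipid panel, medical history and concomitant medications are all scheduled then.

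Count of affected endpoints, taking FRS in 9.2.2.5 to cover both scores named in 9.2.2.2:

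- FRS quantities: 2 scores (10-year CHD, 10-year CVD) × 3 (baseline, week 52, change) = 6.
- Needing a follow-up pressure, under the assumption: 2 × 2 = 4.
- Not needing one: 6 − 4 = 2 (the baseline scores).
- If 9.2.2.5 means change in only one score, the count is 3 of 5: (2 + 1) of (2 + 2 + 1).

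Place in the plan: 3 primary + 4 secondary + 4 exploratory = 11 objectives, of which 0 name FRS. Section 9.4.1 gives baseline descriptive statistics for FRS. Section 9.4.3 compares change in RHI and biomarkers and does not mention FRS.

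**The case against.** The strongest reply is that this is a drafting slip and that sites would take the reading anyway. Clinical assessment is ticked at week 52, vital signs are the first item under that heading in 6.3.6, and the schema describes the 6.1 assessments as including vital signs before sending follow-up to the same section. The week-52 PAT also presupposes some knowledge of systolic pressure. This makes a slip plausible. It does not remove the gap, because every one of these routes ends at a sentence that names two visits and omits week 52.

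A second reply is that the need for measured pressure comes from outside the documents. That is so, and it is why the conclusion is conditional. Without the assumption, it still stands that the plan names a score with neither version nor inputs, so a reader cannot confirm that the week-52 data support it.

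A third reply is that little depends on it: no objective, no power figure and no specified follow-up analysis uses change in FRS. This also stands and sets the weight of the point. Carry-forward and uneven practice between sites are possible consequences; the plan describes neither.

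**Conclusion.** The concern holds as a point to consider. The follow-up FRS endpoints in 9.2.2.2 and 9.2.2.5 have no specified blood pressure input. This rests on the stated assumption that the unnamed version requires measured systolic pressure. Under it, 4 of 6 listed FRS quantities are affected (3 of 5 on the narrower reading of 9.2.2.5).

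The primary endpoint, baseline FRS and the RHI and biomarker analyses in 9.4.3 are not affected. No number of affected participants can be given, because the documents do not show how sites would read the week-52 tick and state no drop-out rate.

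**What to change.** Reconcile 6.3.6, 6.1 and 9.2.2 in one of two ways.

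- **Keep the endpoints.** Amend 6.3.6 so that blood pressure and heart rate are recorded at screening, entry and the week 52/study discontinuation visit, which for HCV-treated participants is the visit after end of treatment. State when the reading is taken relative to PAT, and use the same point at entry and follow-up. Section 6.3.13 interrupts several drug classes before PAT, and the plan fixes no such timing at either visit. Name the FRS version and its inputs in 9.2.2.2. Naming the version alone would not supply the missing reading.
- **Drop them.** Remove week-52 FRS from 9.2.2.2 and change in FRS from 9.2.2.5, keeping the baseline scores.

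The first option costs one reading at an existing visit where a cuff is already applied, a CRF field if none exists (the CRF is not among the documents), and a wording change. The second costs only the wording change. The week-52 reading is what the endpoints need; including the discontinuation visit brings blood pressure into line with waist circumference.

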6.3.7 Concomitant Medications

Initiation and discontinuation of all concomitant medications should be recorded on the CRF with start and stop dates. All ART (including interruption of ART for at least 7 days), HCV treatment (approved or experimental), immune-based and

anti-inflammatory therapy, prescription drugs, vaccines, alternative therapies, dietary supplements, and any experimental therapies taken daily for at least 7 days must be recorded. Changes only in dose or formulation do not need to be recorded.

At the premature study discontinuation visit, record all concomitant medications and ART per above guidelines, including ongoing medications.

6.3.8 Laboratory Evaluations (Note: the majority of these will be collected from the medical records and will not be drawn for the study)

The following must be recorded on CRFs and keyed into the database **unless otherwise indicated**:

Hematology

Hemoglobin, hematocrit, white blood cell count (WBC), absolute neutrophil count (ANC), and platelets within 120 days prior to study entry and **within 120 days prior to the week 52/study discontinuation visit**.

Chemistry

Sodium, potassium, chloride, bicarbonate, blood urea nitrogen (BUN), creatinine, and glucose within 120 days prior to study entry and **within 120 days prior to the week 52/study discontinuation visit**.

Liver Function Tests

Total bilirubin, indirect bilirubin, direct bilirubin, aspartate aminotransferase (AST), alanine aminotransferase (ALT), and alkaline phosphatase, and albumin within 120 days prior to study entry and **within 120 days prior to the week 52/study discontinuation visit**.

INR

INR obtained at a local laboratory within 120 days prior to study and **within 120 days prior to the week 52/study discontinuation visit**.

Pregnancy Test

For women with reproductive potential: Serum or urine beta-human chorionic gonadotropin (β -HCG [urine test must have a sensitivity of at least 50 mIU/mL]) within 28 days prior to study entry and at week 52/study discontinuation visit.

Hepatitis C Antibody Test

For HIV-monoinfected subjects only, screening HCV antibody within 1 year prior to study entry and within 120 days prior to the week 52/study discontinuation visit.

Hemoglobin A1c

For diabetic subjects only, hemoglobin A1c obtained within 180 days prior to study entry and within 120 days prior to the week 52/study discontinuation visit.

6.3.9 Immunologic Studies

CD4+/CD8+ T-cell counts

Absolute CD4+/CD8+ T-cell count and percentages within 12 weeks prior to entry from a laboratory that possesses CLIA certification or an equivalent. CD4 nadir should be recorded on the CRF. At the week 24 and week 52 visits, the medical record should be reviewed and all post-entry values obtained since the last study visit should be recorded.

6.3.10 Virologic Studies

Plasma HIV-1 RNA

Plasma HIV-1 RNA level within 12 weeks prior to study entry and within 28 days of week 52/**study discontinuation** visit, at any laboratory that has CLIA certification or its equivalent.

Subjects who switch their ART regimen prior to study entry (see 4.1.6) should have an HIV-1 RNA level performed while on the new regimen, prior to study entry. Record post-entry values obtained as part of routine care.

The requirement of plasma HIV-1 RNA level within 28 days of the week 52/study discontinuation visit is waived for subjects that meet ALL of the following criteria:

- 1) HIV-1 RNA <50 copies/mL on all laboratory testing in the preceding 2 years**
- 2) HIV-1 RNA <50 copies/mL in the preceding 90 days**
- 3) No change in ART regimen since study entry**
- 4) No ART interruption of more than 7 consecutive days or 14 total days in the preceding 90 days**
- 5) No HCV treatment since study entry**

For subjects who meet ALL of the above criteria, the most recent HIV-1 RNA level from the medical record, closest to the time of the week 52/study discontinuation visit, is acceptable.

Serum HCV RNA (screening)

At screening, the HCV RNA result must be obtained by any FDA-approved test for quantifying HCV RNA at any local laboratory that has a CLIA certification or its equivalent. Screening HCV RNA at any point prior to study entry is acceptable, in the absence of intervening treatment.

Serum HCV RNA (on-study evaluations)

At the week 24 and week 52 visits, the medical record should be reviewed and all post-entry values obtained since the last study visit should be recorded.

Coinfected subjects who begin HCV treatment should have HCV RNA testing at 4 weeks after EOT (“week 52” visit), but no earlier than 3 weeks and no later than 8 weeks after EOT. This may be abstracted from the medical record and if not done, should be performed using a CLIA-certified or equivalent laboratory. The medical record should be reviewed and HCV RNA at weeks 12 and 24 after EOT should be documented.

HCV Genotype Test

A documented result (serum or plasma) is a source document from a CAP/CLIA-approved laboratory at any time prior to entry. For those subjects lacking a documented result, HCV genotyping should be performed by a local CAP or CLIA-approved (or its equivalent) laboratory.

